#### **4.4 Sensitivity Analysis and Handling of Missing Data**

The proportion of subjects with SSO up to 45-days along with 95% confidence interval will be estimated using the Kaplan-Meier method. Number of subjects with events, number of subjects censored and number of subjects left will also be presented.

The time to first event will be the time from index-procedure to the occurrence of the first event. Subjects who do not have a SSO before 45 days and do not discontinue the study before day 45 will be censored at day 45; subjects who discontinue before day 45 will be censored by their discontinuation day. If subjects discontinue at the surgery day then day 0.5 will be used as censor date. Note, the circumstances may be described separately.

A Kaplan-Meier graph will also be provided showing the survival curves for female and males separately.

Additionally, sensitivity analysis will be performed using PP population (if created).

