## **4 Primary Endpoints**

The primary endpoint is Surgical Site Occurrence (SSO) up to (and including) 45 days post implantation.

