### **4.3 Primary Analysis**

The proportions of subjects with SSO up to 45-days, and 95% confidence intervals of the rate from exact binomial test, will also be reported. Primary analysis is based on mITT population.

Reported start date of the SSO minus the date of the index hernia repair (implantation of the Phasix™ ST) will be used to determine if a SSO occurred within 45 days from index surgery. Any subjects discontinued before 45 days that do not have an SSO are considered as not evaluable and will be excluded from the analysis.

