### **5 Evaluation of Secondary Endpoints**

#### **5.1 Surgical Site Occurrence (SSO) > 45-days follow-up assessment**

The proportion of subjects with SSO >45 days post-operatively (including all events post day 45 that are available at the time of the final report) and confidence intervals of the rate from exact binomial test will be reported.

If a subject discontinued within ( $\leq$ ) 45 days after index surgery, that subject is considered not evaluable and will be excluded from calculation of SSO rate after 45 days follow-up.

Analysis is based on mITT population.

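### The Kaplan-Meier censoring clause in SAP 4.4 stops short of day 45, so read literally it censors an SSO that starts on day 45, which SAP 4 counts as a primary event

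*SAP*

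**What the plan says.** Four places in the SAP bear on the day-45 boundary.

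- **Section 4** includes day 45 in the primary window: "The primary endpoint is Surgical Site Occurrence (SSO) up to (and including) 45 days post implantation".
- **Section 4.3** reports "The proportions of subjects with SSO up to 45-days, and 95% confidence intervals of the rate from exact binomial test". The event day is a difference of dates: "Reported start date of the SSO minus the date of the index hernia repair". The result is a whole number of days, so exactly 45 is a possible value.
- **Section 4.4** states the Kaplan-Meier target in matching terms: "The proportion of subjects with SSO up to 45-days along with 95% confidence interval will be estimated using the Kaplan-Meier method". It defines event time as the time from the index procedure to the first event, and then gives the censoring rule: "Subjects who do not have a SSO before 45 days and do not discontinue the study before day 45 will be censored", at day 45. The sentence goes on: "subjects who discontinue before day 45 will be censored by their discontinuation day". Discontinuation on the day of surgery is set to day 0.5.
- **Section 5.1** defines the late endpoint as "The proportion of subjects with SSO >45 days post-operatively". Day 45 therefore belongs to the primary window only.

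**The concern.** A subject with a first SSO on day 45 who remains in the study meets both conditions of the censoring rule in section 4.4: no SSO earlier than day 45, and no discontinuation earlier than day 45. A programmer who follows the sentence as written assigns that subject the status censored. The same subject is in the numerator in section 4.3 and is not picked up by section 5.1.

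The Kaplan-Meier estimate is the only planned analysis of the primary endpoint that treats early dropout differently from the primary analysis. Section 4.3 excludes subjects who leave early without an SSO; section 4.4 keeps them until they leave. The per-protocol analysis does not address dropout. The Kaplan-Meier result is useful mainly in comparison with section 4.3, so the two should classify every event in the same way. The misclassification can only lower the Kaplan-Meier rate.

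**Working it through.** **No figure to reproduce.** The plan gives no expected SSO rate, power or precision. Both documents say that the sample size of about 120 has no statistical basis. The sizes below rest on N = 120 from the documents and on stated assumptions.

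**Step 1: a first SSO on day 45, under each section**

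| Place | Rule | SSO starting on day 45 |
|---|---|---|
| SAP 4 and 4.3 | day ≤ 45 | event |
| SAP 4.4, stated target | up to 45 days | event |
| SAP 4.4, censoring clause | no SSO on day < 45 | censored at day 45 |
| SAP 5.1 | day > 45 | not counted |

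Only the censoring clause disagrees.

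**Step 2: size without dropout.** Let S be the Kaplan-Meier survival just before day 45 and n the number at risk on day 45. One event on day 45 adds S/n to the estimated SSO rate. With no dropout S = n/120, so the loss from censoring that event is 1/120 = 0.83 points. Assume 12 SSOs in total:

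- No SSO on day 45: both readings give 12/120 = 10.00%.
- One on day 45: inclusive 12/120 = 10.00%, literal 11/120 = 9.17%, difference 0.83 points.
- Two on day 45: inclusive 10.00%, literal 10/120 = 8.33%, difference 1.67 points.

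The loss is 0.83 points per event at 6, 18 or 24 SSOs as well, since it does not depend on the total.

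**Step 3: size with dropout.** Assume 10 subjects leave on day 30 without an SSO, and 12 SSOs occur: 8 before day 30, 3 between days 30 and 45, and 1 on day 45.

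- Survival just before day 45: (112/120) × (99/102) = 0.9059.
- Literal rule: 1 − 0.9059 = 9.41%.
- Inclusive rule: 1 − 0.9059 × (98/99) = 10.33%.
- Difference: 0.9059/99 = 0.92 points.

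With 5 dropouts the loss is 0.87 to 0.88 points per event over 6 to 24 SSOs.

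**Step 4: how likely is an SSO on exactly day 45?** The documents give no onset distribution. With true rate p and a share w of onsets falling on day 45, the chance of at least one is 1 − (1 − p·w)^120.

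| Assumed onset over 45 days | p = 5% | p = 10% | p = 20% |
|---|---|---|---|
| Uniform (w = 1/45) | 12.5% | 23.4% | 41.4% |
| Front-loaded, exponential with mean 15 days | 2.1% | 4.2% | 8.3% |
| Front-loaded, exponential with mean 10 days | 0.7% | 1.4% | 2.8% |

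**Step 5: scale.** For 12/120 the exact 95% interval is 5.3% to 16.8%, and the Kaplan-Meier standard error is 2.74 points, so one misclassified event is about 0.83/2.74 = 0.3 standard errors. The genuine dropout effect can be just as small. With 12 SSOs (9 before day 30, 3 after, none on day 45) and 10 dropouts on day 30, the primary rate is 12/110 = 10.91%. The Kaplan-Meier rate is 1 − (111/120) × (98/101) = 10.25%. That gap of 0.66 points is what the sensitivity analysis is meant to show.

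**The case against.** The strongest reply is that this is one boundary word. Section 4.4 opens with the right target, the effect is zero unless an onset falls on one particular day, the primary result does not move, and the study has no hypothesis or threshold that a change of 0.8 points could cross. A careful programmer would probably code day ≤ 45. All of this stands, and it limits the point to a minor one. It does not make the sentence correct. The usual convention that events precede censorings tied on the same day does not help either, because the rule sets the subject's status to censored.

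Three stronger readings are tempting, and the documents do not support them.

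- *The Kaplan-Meier analysis estimates a different quantity from the primary analysis.* It does not. Section 4.4 gives it the same target as section 4.3, and the sentence at issue is a censoring rule, not an event definition.
- *The discontinuation clause also drops events, because it does not exempt subjects who had an SSO before they left.* Section 4.4 defines time to first event, so an SSO on day 10 already fixes the event time of a subject who leaves on day 30. Section 4.3 draws the same distinction: it excludes early leavers only if they had no SSO. Losing such events would require coding against that definition. A clarifying phrase is still worthwhile, because protocol 6.5 allows withdrawal after surgery that affects the repair site, so an SSO followed by early withdrawal can occur.
- *A dropped event would pass unnoticed as a dropout effect.* Section 4.4 requires the numbers of events and censored subjects to be shown. A lost event would appear as an event count below the primary numerator, which dropout alone does not cause.

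**Conclusion.** The inconsistency is real and confined to one clause. Followed literally, SAP 4.4 censors an SSO that starts exactly on day 45, although section 4 makes it a primary event and section 5.1 leaves it out of the late endpoint. At N = 120 the Kaplan-Meier rate falls by 0.83 points per such event without dropout, and by about 0.9 points with 5 to 10 dropouts. It falls by nothing if no SSO starts on that day. The exact-binomial primary analysis is unaffected.

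The loss per event depends only on N and the assumed dropout. The chance that it arises depends on onset timing, which the documents do not give: roughly 1% to 8% if onsets are front-loaded and 12% to 41% if they are uniform, for true rates of 5% to 20%. Severity is minor. The rule is wrong as written, but little depends on it.

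**What to change.** Replace the censoring sentences in SAP 4.4 with:

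> *Subjects with an SSO on or before day 45 are events at the start day of the first SSO, regardless of later discontinuation. Subjects without an SSO on or before day 45 are censored at day 45 or, if they discontinue before day 45, at their discontinuation day (day 0.5 if on the day of surgery).*

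The phrase on later discontinuation is a clarification that matches section 4.3. Sections 4.3 and 5.1 need no change. In the program, derive the day ≤ 45 event flag once and use it for both section 4.3 and section 4.4, so that the two event counts agree.

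The cost is two sentences and one derivation, with no new data. The change is best made before the interim analysis described in SAP section 1, which is run once all subjects have reached 45 days or have withdrawn.

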### **5 Evaluation of Secondary Endpoints**

#### **5.1 Surgical Site Occurrence (SSO) > 45-days follow-up assessment**

The proportion of subjects with SSO >45 days post-operatively (including all events post day 45 that are available at the time of the final report) and confidence intervals of the rate from exact binomial test will be reported.

If a subject discontinued within ( $\leq$ ) 45 days after index surgery, that subject is considered not evaluable and will be excluded from calculation of SSO rate after 45 days follow-up.

Analysis is based on mITT population.

#### **5.2 Hernia Recurrence Rate**

The proportion of subjects with Hernia Recurrence and confidence intervals of the rate from exact binomial test will be reported by each visit window, including both cumulative (overall rate) and disjointed intervals.

The start date of the hernia recurrence minus the implantation date will determine the interval of hernia recurrence.

Only evaluable subjects will be included in the denominator and evaluable subjects are defined as following: 1) For cumulative intervals, any subjects with Phasix™ ST Mesh implanted will be included in this analysis. 2) For disjointed intervals, if a subject discontinues before the intervals begins then that subject is considered as not evaluable for that particular interval analysis. Note: if subject did not come for a scheduled clinical visit (of the report period), but it was known that the subject was in the study and did not report hernia recurrence during the respective time interval, then the subject will be considered as free from the recurrence.

Hernia Recurrence in the same location as index procedure is identified by physical exam or any other means from post-operative CRF pages at scheduled or unscheduled visits. Analysis is based on mITT population (all subjects implanted with Phasix™ ST Mesh).

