Laparoscopic ventral hernia repair was first reported by LeBlanc in 1992, and is popular alternative to open repairs due to the potential benefit of shorter hospital stays, improved patient outcomes, and fewer complications compared to open repairs.^{14, 15} In a large series (850 patients) by Heniford, et al., laparoscopic ventral hernia repair using prosthetic mesh had a low rate of conversion to open surgery (3.4%), length of hospital stay (2.3 days), a moderate complication rate (13.2%), and a low hernia recurrence rate of 4.7% (average follow-up of 20 months).¹⁵ In a study by Orenstein, et al., laparoscopic ventral hernia repair with defect closure had a low recurrence rate (none in 47 consecutive patients out to 16.2 months follow-up).¹⁶ They purported that defect closure eliminated postoperative seromas and patient reports of bulging and reduced the size of implanted mesh.¹⁶

Ideally, a resorbable mesh would provide adequate structural support throughout the healing process and would be fully absorbed when the wound has completely healed, thereby potentially reducing the chances for complications associated with the persistence of non-resorbable mesh material. However, the development of resorbable mesh products has faced

challenges related to the rate of resorption with complications arising when the mesh product is resorbed too quickly. Rapid resorption does not support sufficient healing if structural reinforcement is diminished during the tissue repair period. A resorbable mesh should retain its functional strength for a sufficient period of time to allow native cellular ingrowth tissue remodeling, maturation of collagen, and gradual shift of mechanical load.

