Appendix 2: Surgical Site Infection Classification²⁴

Superficial Incisional Surgical Site Infections (SSI)

Infection occurs within 30 days after the operative procedure (where day 1 = procedure day)

AND

involves only the skin or subcutaneous tissue of the incision

AND

at least one of the following:

- A. Purulent drainage from the superficial incision or subcutaneous tissue.
- B. Organisms isolated from an aseptically obtained culture of fluid or tissue from the superficial incision.
- C. Superficial incision that is deliberately opened by a surgeon, attending physician or other designee and is culture positive or not cultured
AND
Patient has at least one of the following signs or symptoms: pain or tenderness; localized swelling; erythema; or heat. A culture negative finding does not meet this criterion.
- D. Diagnosis of a superficial incisional SSI by the surgeon or attending physician or other designee.

COMMENT: There are two specific types of superficial incisional SSIs:

1. Superficial Incisional Primary (SIP) –a superficial incisional SSI that is identified in the primary incision in a patient that has had an operation with one or more incisions (e.g., C -section incision or chest incision for CBGB)
2. Superficial Incisional Secondary (SIS) – a superficial incisional SSI that is identified in the secondary incision in a patient that has had an operation with more than one incision (e.g., donor site incision for CBGB)

The following do not qualify as criteria for meeting the definition of superficial SSI:

- Diagnosis/treatment of cellulitis (redness/warmth/swelling), by itself, does not meet criterion d for superficial incisional SSI. An incision that is draining or culture (+) is not considered a cellulitis.
- A stitch abscess alone (minimal inflammation and discharge confined to the points of suture penetration).

Deep Incisional SSI

Infection occurs within 90 days after the operative procedure (for herniorrhaphy)(where day 1 = procedure day)

AND

involves deep soft tissues of the incision (e.g., fascia and muscle layers)

AND

patient has at least one of the following:

- a. Purulent drainage from the deep incision.

b. A deep incision spontaneously dehisces or is deliberately opened or aspirated by a surgeon, attending physician or other designee and is culture positive or not cultured
AND

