## **6        Subgroup Analysis**

By sex subgroup analysis will be performed for primary and Kaplan-Meier analysis (tables and curves) for primary and some secondary endpoints.

Where appropriate, further subgroup analysis (based on the mITT set) may be performed for the primary endpoint if enough subjects within the subgroups allow further insight to the data. Following subgroups are subject to further interest:

- Investigational Sites.
- Type of Procedure: Laparoscopic only versus Robotic Assisted.
- Surgical Technique: ‘Retro-rectus with CST’, ‘Retro-rectus without CST’, ‘Intra-Abdominal with CST’, ‘Intra-Abdominal without CST’ and ‘Other’.

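### The cumulative recurrence and reoperation rates keep every implanted subject in the denominator to month 24, so they are biased low whenever subjects leave alive and event-free

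*SAP*

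**What the plan says.** SAP 5.2 reports recurrence as a proportion with an exact binomial interval for each visit window, both cumulatively and for disjoint intervals. It limits the denominator to evaluable subjects and then defines them in two ways. For the overall rate: "For cumulative intervals, any subjects with Phasix™ ST Mesh implanted will be included in this analysis". For the disjoint rates: "if a subject discontinues before the intervals begins then that subject is considered as not evaluable for that particular interval analysis". SAP 5.5 repeats both rules for reoperation.

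A further rule in 5.2 covers a missed visit. If the subject is known to be still in the study and has reported no recurrence, "then the subject will be considered as free from the recurrence". This does not reach subjects who have left.

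Elsewhere the plan treats leavers differently:

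- SAP 4.3 excludes from the primary analysis subjects who discontinue before day 45 without an SSO.
- SAP 4.4 adds a Kaplan-Meier estimate in which "subjects who discontinue before day 45 will be censored by their discontinuation day".
- SAP 5.1, for late SSO, says of a subject who discontinued by day 45 that "that subject is considered not evaluable and will be excluded from calculation of SSO rate after 45 days follow-up".
- Protocol 7.3 bases rates on the data available at each time point, without imputation, and adds a Kaplan-Meier analysis. Both statements stand in the paragraph on the primary endpoint.
- SAP 6, after announcing a by-sex analysis, refers to "Kaplan-Meier analysis (tables and curves) for primary and some secondary endpoints" without saying which secondary endpoints are meant.

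**The concern.** Someone lost at month 2 has not been observed to be free of recurrence at month 24, yet the cumulative rate counts that person as a non-event there. The 45-day endpoint, where little loss can build up, has a censoring-adjusted estimate. The two 24-month endpoints, where loss builds up most, have none that is named.

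The study is single-arm with no formal hypothesis, so the reported rates are its product. Recurrence is followed through 24 months for a mesh whose fibres, by Protocol 1.3.1, degrade significantly within 12 to 18 months. The error can only make the rate look lower, and it is largest at the last window. At stake is a reported rate that is too low, not a changed trial decision.

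**Working it through.** The plan has no figure to reproduce: the 120 subjects have no statistical basis, and no recurrence, reoperation or dropout rate is planned. The check applies the SAP rule directly.

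**Direction.** Let N be the number implanted, x the events seen, and u the events among leavers after they left.

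- Rate reported: x / N.
- Rate under full follow-up: (x + u) / N, with u ≥ 0.

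The reported rate cannot exceed the full-follow-up rate, whether or not loss is related to risk. It is lower in expectation whenever some subjects leave alive and event-free and still carry risk. With no such loss there is no bias. A subject who dies event-free is a true non-event for cumulative incidence and is not part of this point.

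**Inputs for the size.**

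- N = 120 (SAP 2.4).
- Windows to 24 months (SAP 2.3).
- True 24-month risk p: assumed 4.7%, 10% or 15%. The first borrows the background figure for a cited laparoscopic series, "a low hernia recurrence rate of 4.7% (average follow-up of 20 months", as a scenario only. At constant hazard, 4.7% at 20 months is 1 − 0.953^(24/20) = 5.6% at 24 months.
- Fraction d lost alive by month 24: assumed 10%, 20% or 30%.
- Confidence level: taken as 95%; SAP 5.2 and 5.5 do not state it.

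**Formula.** With constant hazard λ = −ln(1 − p)/24 and loss times uniform over 0 to w months:

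expected crude rate = (1 − d)·p + d·m, where m = 1 − (1 − e^(−λw))/(λw).

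For p = 15%, d = 20%, w = 24: m = 1 − 0.15/0.1625 = 0.0770, so the crude rate is 0.8 × 0.15 + 0.2 × 0.0770 = 13.5%. For p = 4.7%: m = 0.0237, so 0.8 × 0.047 + 0.2 × 0.0237 = 4.2%.

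**Expected crude rate at month 24, and coverage of the 95% exact interval, for d = 10/20/30%:**

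| True risk | Loss over | Reported rate, % | Coverage, % |
|---|---|---|---|
| 4.7% | 24 months | 4.5 / 4.2 / 4.0 | 96.6 / 96.0 / 95.2 |
| 10% | 24 months | 9.5 / 9.0 / 8.5 | 96.8 / 96.1 / 94.7 |
| 15% | 24 months | 14.3 / 13.5 / 12.8 | 95.4 / 93.9 / 91.0 |
| 4.7% | first 12 months | 4.35 / 4.00 / 3.65 | 96.2 / 95.3 / 93.7 |
| 15% | first 12 months | 13.9 / 12.8 / 11.7 | 94.9 / 91.2 / 84.1 |

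Coverage is from simulation (40,000 replicates); exact binomial calculation agrees to within 0.3 points. In events per 120, even loss hides 0.3/0.6/0.8 at 4.7% and 0.9/1.8/2.6 at 15%.

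**Growth over time.** With even loss the relative understatement is about 1.2/2.5/3.7% at month 6, 2.5/5.0/7.5% at month 12, 3.7/7.5/11% at month 18 and 5/10/15% at month 24.

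**Under the alternative.** In the same simulation the Kaplan-Meier estimate at 24 months averaged 4.7%, 10.0% and 15.0%, with coverage of 95.1 to 96.8% (replicates with at least one event; loss independent of risk). A worked case: 120 implanted and, in each of six windows, four event-free losses at the start and then two recurrences. Crude: 12/120 = 10.0%. Kaplan-Meier: 1 − (114/116)(108/110)(102/104)(96/98)(90/92)(84/86) = 11.4%.

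**Windows without events.** At a true 4.7% with no loss, the chance of no event among 120 is 0.953^(120t/24) by month t: 0.953^5 = 79% at month 1, 0.953^15 = 49% at month 3 and 0.953^30 = 24% at month 6. The Kaplan-Meier interval is undefined there; the exact binomial interval is not.

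**The case against.** Several arguments on the other side carry weight.

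- **Materiality.** At 4.7% with even loss the error is under one event in 120 and coverage stays at or above 95%. This stands and limits the point.
- **Assumed dropout.** The loss fractions have no basis in the documents, and the protocol has retention measures: exclusion of subjects who could not complete follow-up, three contact attempts before a subject counts as lost, an early-termination visit, and possible visit stipends. This stands for the size, not the direction.
- **Choice of target.** Recurrence is defined as a hernia found at a study visit, so events over implanted is a transparent count of observed recurrences. It is, and it should be kept. But labelled as an overall 24-month rate it will be read as a risk, and for that it is a lower bound.
- **Handled elsewhere.** The disjoint rates drop prior leavers, and disposition and follow-up duration are reported, so attrition is visible. However, the SAP does not combine the disjoint rates into an overall rate, and SAP 6 names neither endpoint.
- **Kaplan-Meier has limits.** It assumes non-informative loss. Protocol 6.5 allows withdrawal after surgery affecting the repair site, which may be informative; if leavers are at lower risk, the estimate is too high. It also gives no usable interval before the first event. Both objections stand and shape the fix.

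A reader might infer that the study's main result is compromised, or that the planned intervals are generally invalid. The documents support neither. The primary endpoint has its own exclusion and censoring rules, no hypothesis depends on these rates, and coverage falls clearly below 95% only at higher true rates or with heavy or early loss. Nor do they support dropping the exact intervals. SAP 5.4, 5.9 and 5.10 also report cumulative rates but state no denominator rule, so the same fault cannot be asserted there.

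**Conclusion.** The point holds and should be fixed. The overall recurrence and reoperation rates in SAP 5.2 and 5.5 are biased low whenever subjects leave alive and event-free. The direction is certain and does not depend on why they leave.

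The size rests wholly on assumed loss. Under constant hazard it is roughly half the loss fraction in relative terms if loss is even over 24 months, and about 7/15/22% for 10/20/30% loss if all of it falls in the first 12 months. In points at month 24 with even loss, that is 0.2/0.5/0.7 at a true 4.7% and 0.7/1.5/2.2 at 15%. The consequence is confined to descriptive secondary rates.

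Late SSO (SAP 5.1) has a lesser form of the same feature, since subjects who leave after day 45 count as free of it. The effect is likely small: if late events fall between day 45 and day 90, it is 0.3/0.7/1.0% relative. Day 90 is the limit that Protocol Appendix 2 sets for deep and organ/space infection ("Infection occurs within 90 days after the operative procedure"); applying it to all late SSO is an assumption.

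**What to change.** In SAP 5.2 and 5.5, and by name in SAP 6:

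1. Report overall cumulative recurrence and reoperation as 1 − Kaplan-Meier with 95% CI and numbers at risk, censored at discontinuation as in SAP 4.4. If deaths occur, report cumulative incidence with death as a competing event. With assumed 24-month mortality of 2% or 5% and a true 4.7%, 1 − Kaplan-Meier would be about 1.1% or 2.5% too high in relative terms.
2. Keep crude n/N over all implanted, with its planned exact binomial interval, beside it and labelled a lower bound under loss. Use that exact interval at windows with no events.
3. State that the Kaplan-Meier estimate assumes non-informative loss. Add a sensitivity analysis censored at the last assessment of status, which also tests the missed-visit rule in 5.2.

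Doing the same for late SSO, starting at day 45, is optional.

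The cost is SAP wording and a few more tables, with no new data. Rates will be slightly higher and intervals slightly wider: with 20% even loss, the mean 95% CI width at month 24 is 8.8 rather than 8.0 points at a true 4.7%, and 13.7 rather than 12.9 at 15%.

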6.5 Withdrawal and/or Early Termination

Subjects will be informed that they have the right to withdraw from the study at any time, without affecting their future care.

Additionally, subjects may be discontinued for reasons including, but not limited to the following:

- Consent is withdrawn
- Lost to follow-up (LTFU)
- Investigator withdrawal of subject
- Other

A subject is considered LTFU if the investigational site personnel are unable to locate the subject despite two documented attempts to notify the subject via telephone and a third attempt by certified mail.

A subject is considered an Early Termination (ET), if discontinuation occurs after successful implant of the study device. The site should attempt to bring the subject back to complete all ET visit study procedures (see Table of Study Events).

A subject who receives a re-operation due to hernia recurrence or has the repair site surgically impacted in any way, may be withdrawn from the study upon discharge from the most recent hospitalization. Site personnel will be responsible for documenting adverse events and other post-procedural complications on the applicable eCRF that the subject may have encountered during the hospitalization and up to 30 days post re-operation.

Once a subject discontinues from the study, the Investigator must complete a Study Completion eCRF and the reason for subject discontinuation must be fully documented.

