### **5.5 Rate of Reoperation due to Index Hernia Repair**

The proportion of subjects with reoperation due to the index hernia repair and confidence intervals of the rate from exact binomial test will be reported by visit, including both cumulative and disjoint intervals.

Reoperation date will be compared to surgery date to determine the interval of reoperation.

Only evaluable subjects will be included in the denominator and evaluable subjects are defined as following: 1) For cumulative intervals, any subjects with Phasix™ ST Mesh implanted will be included in this analysis. 2) For disjoint intervals, if a subject discontinues before the intervals begins then that subject is considered as not evaluable for that particular interval analysis. Analysis is based on mITT population.

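### SAP 5.2 keeps subjects who have already recurred in later disjoint-interval denominators, so late first-recurrence rates come out too low; for reoperation (SAP 5.5) this depends on what is counted

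*SAP*

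**What the plan says.** SAP 5.2 reports recurrence by visit window in two ways, cumulatively and in disjoint intervals, with exact binomial confidence intervals. Events are placed by date: "The start date of the hernia recurrence minus the implantation date will determine the interval of hernia recurrence". For the cumulative rate the denominator is everyone implanted: "For cumulative intervals, any subjects with Phasix™ ST Mesh implanted will be included in this analysis". For the disjoint rate the only stated exclusion is "if a subject discontinues before the intervals begins then that subject is considered as not evaluable for that particular interval analysis". A subject who misses a visit but is known to be in the study, with no recurrence reported in that interval, stays in: "then the subject will be considered as free from the recurrence".

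SAP 5.5 uses the same structure for reoperation: "Reoperation date will be compared to surgery date to determine the interval of reoperation", and "For disjoint intervals, if a subject discontinues before the intervals begins then that subject is considered as not evaluable".

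Neither section removes a subject who has already had the event, and neither says whether the numerator is limited to first events.

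Protocol 6.5 adds an optional exit: "A subject who receives a re-operation due to hernia recurrence or has the repair site surgically impacted in any way, may be withdrawn". It gives no criterion for when this is done.

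**The concern.** A rate for a disjoint interval is normally read as the risk in that interval among those who could still have the event. Under SAP 5.2, a subject with an unrepaired recurrence at month 6 who stays in follow-up cannot have a first recurrence at 12, 18 or 24 months, yet is in all three denominators. A subject with the same recurrence who is reoperated and withdrawn is in none of the windows that begin after the withdrawal. The reported rate therefore depends partly on an optional withdrawal.

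For first recurrence the error runs one way, towards a lower rate. Prior events accumulate, so it is largest in the late windows unless those subjects are withdrawn. These are also the windows of most interest: the protocol's preclinical background (1.1 and 1.3.1) places essentially complete resorption, or significant degradation, of the mesh fibres at 12 to 18 months, so the 18- and 24-month windows show whether the repair outlasts the mesh.

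**Working it through.** There is no planned figure to reproduce. Protocol 7.2 and SAP 2.4 say that the 120 subjects rest on no statistical consideration, and neither document plans a recurrence or reoperation rate.

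**Formula.** Let *n* be the subjects not discontinued at the start of an interval, *p* those of the *n* who already had the event, and *x* the first events in the interval.

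- SAP rate = *x* / *n*
- At-risk rate = *x* / (*n* − *p*)
- SAP rate ÷ at-risk rate = 1 − *p*/*n*

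The relative understatement is therefore the share of the denominator that already had the event.

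**Inputs.** From the documents: *N* = 120; six post-operative visits; background recurrence figures of 4.7% (a laparoscopic series, average follow-up 20 months) and up to 46% (large abdominal wall defects), both in Protocol 1.1 and neither a planning value. Assumed: cumulative recurrence of 10% and 20% as intermediate scenarios; about one sixth of events in the last of six windows; first events only; no other dropout; no withdrawal after the event; 95% intervals, since SAP 5.2 states no level.

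**Last window.**

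| Cumulative recurrence | Total events | Last window *x* | Prior *p* | SAP rule *x*/120 (95% CI) | At risk *x*/(120 − *p*) (95% CI) | Ratio | Gap, points |
|---|---|---|---|---|---|---|---|
| 4.7% | 6 | 1 | 5 | 1/120 = 0.83% (0.02–4.56) | 1/115 = 0.87% (0.02–4.75) | 0.958 | 0.04 |
| 10% | 12 | 2 | 10 | 2/120 = 1.67% (0.20–5.89) | 2/110 = 1.82% (0.22–6.41) | 0.917 | 0.15 |
| 20% | 24 | 4 | 20 | 4/120 = 3.33% (0.92–8.31) | 4/100 = 4.00% (1.10–9.93) | 0.833 | 0.67 |
| 46% (extreme) | 55 | 9 | 46 | 9/120 = 7.50% (3.49–13.76) | 9/74 = 12.16% (5.71–21.84) | 0.617 | 4.66 |

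**Withdrawal after the event.** If about half of the prior-event subjects are withdrawn, the SAP figures rise to 1/118 = 0.85%, 2/115 = 1.74%, 4/110 = 3.64% and 9/97 = 9.28%. If all are withdrawn, the two denominators coincide and the gap is zero.

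**Other dropout.** If 20% of the 120 (24 subjects), all event-free, have left before the last window, *n* = 96 and the pairs are 1/96 = 1.04% vs 1/91 = 1.10%, 2/96 = 2.08% vs 2/86 = 2.33%, 4/96 = 4.17% vs 4/76 = 5.26%, and 9/96 = 9.38% vs 9/50 = 18.00%. Event-free dropout widens the gap because prior events become a larger share of those who remain.

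**Cumulative rate.** Its denominator is all implanted subjects, so the disjoint-interval rule does not enter it.

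**The case against.** The strongest reply is that the SAP never limits the numerator to first events. Where it wants first events it says so, as in 4.4 for the primary endpoint. If a disjoint interval is meant to show every subject with an event in that interval, a subject who can have another one belongs in the denominator. This stands for reoperation, which can be repeated, and for recurrence after a re-repair. A reader might infer that late reoperation rates are understated just as late recurrence rates are; the documents do not support that, because 5.5 does not say which reoperations are counted. The reply does not cover an unrepaired recurrence, which has one start date, falls in one interval and cannot be a new first recurrence later.

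A second reply concerns size. A reader might infer a large distortion, or one that reaches the overall recurrence rate. The cumulative rate, which 5.2 treats as the overall one, is untouched by this rule. At the laparoscopic background rate of 4.7% the last-window shift is 0.04 points, and up to 20% it is small against the confidence interval. Withdrawal after reoperation reduces it further. All of this stands.

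Third, the study tests no hypothesis, these are descriptive rates for secondary endpoints, and SAP 6 foresees Kaplan-Meier analysis for some secondary endpoints. That lowers the stakes. It does not repair the rule, since SAP 6 names neither recurrence nor reoperation.

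**Conclusion.** The concern holds for disjoint-interval rates of first recurrence. The stated rule keeps subjects in the denominator who can no longer have the event, and it makes the rate depend on an optional withdrawal. The error favours the device, with a relative size equal to the share of the denominator that has already recurred: about 4%, 8% and 17% in the last window at 4.7%, 10% and 20% cumulative recurrence.

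These figures rest on first-event counting, 120 subjects, no other dropout, no withdrawal after the event and one sixth of events in the last window. They are scenarios and not predictions. Withdrawal after the event brings the gap towards zero, and event-free dropout enlarges it. The 46% scenario is an extreme, taken from a background figure for large defects.

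For reoperation, and for recurrence after re-repair, there is understatement only if first events alone are counted. The point is worth correcting because the direction is known, the late windows matter for a resorbable mesh, and no new data are needed.

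**What to change.** **SAP 5.2.** Report the disjoint intervals for first recurrence. Define the denominator as implanted subjects who are in follow-up and recurrence-free at the start of the interval. Preferably give these as life-table or Kaplan-Meier conditional probabilities, with censoring at discontinuation as SAP 4.4 already does for the primary endpoint. That also deals with subjects who leave during an interval, whom the present rule counts as fully observed.

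**SAP 5.5.** State whether first or any reoperation is counted. Use the event-free denominator only for first reoperation; if any reoperation counts, subjects with an earlier one stay in.

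No change to the withdrawal provision in Protocol 6.5 is needed for this.

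**Cost.** About a sentence in each of the two sections, using dates already collected. The late-interval rates will be slightly less favourable and their confidence intervals slightly wider; in the 20% scenario the interval goes from 0.92–8.31% to 1.10–9.93%.
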